12.5.4.4 Clinical Laboratory Evaluation

Table 20 below lists the hematology, clinical chemistry and urine analysis parameters to be assessed in this study.

Hematology	Clinical Chemistry	Urine Analysis
Hematocrit	Albumin	pH
Hemoglobin	Total protein	Bilirubin
Mean corpuscular hemoglobin	Alkaline phosphatase	Glucose
Mean corpuscular hemoglobin concentration	Alanine aminotransferase	Nitrite
Mean corpuscular volume	Aspartate aminotransferase	Red blood cell traces
Platelet count	Blood urea nitrogen	Protein
Red blood cell count	Creatinine	Specific gravity
White blood cell (WBC) count	Gamma-glutamyl transferase	Urine sediment
Differential WBC count:	Fasting glucose	
• Neutrophils	Lactate dehydrogenase	
• Basophils	Potassium	
• Eosinophils	Sodium	
• Lymphocytes	Total bilirubin	
Monocytes	Direct bilirubin	
	Total cholesterol	
	Triglycerides	

Any clinical safety laboratory test result that is outside of the normal reference range will be reviewed by the PI and assessed for clinical relevance. If the PI considers the abnormal result to be of clinical relevance, then it must be recorded as a concomitant disease at Screening, or if not present at Screening, as an AE during the study. If the condition worsens from screening to after product-use it will be recorded as an AE.

The grading scheme used in the Common Terminology Criteria for Adverse Events and Common Toxicity Criteria [CTCAE] version 4.03) will be used by the PI to assess abnormal laboratory AEs. These CTCAE grades will be derived programmatically in the creation of the datasets.

Laboratory data will be summarized and listed by product, subject, parameter and time point at Screening, Day -1 and at Day of Discharge (Day 6 or day of withdrawal), together with numerical changes from baseline. The number and percentage of subjects with normal results, high/low results and abnormal clinical result (as defined by PI comment) will be tabulated for laboratory parameters.

Listings for the clinical laboratory data will include the following information: normal/high/low (with respect to the reference range), abnormal clinically relevant (as defined by the PI comments), the PI comments, the change from baseline and the CTCAE grade. Only CTCAE grades greater than zero will be presented

The data will be presented in the below outputs, the TFL number refers to the TFL number in the accompanying TFL shell document:

TFL number	Title
TABLES	
15.2.6.13	Summary of Clinical Chemistry Parameters – Safety Population
15.2.6.14	Summary of Hematology Parameters – Safety Population
15.2.6.15	Summary of Urinalysis Parameters – Safety Population
LISTINGS	
15.3.6.4	Listing of Clinical Chemistry Data, Shift, Changes from Baseline and CTCAE grades
15.3.6.5	Listing of Hematology Data Shift, Changes from Baseline and CTCAE grades
15.3.6.6	Listing of Urinalysis Data Shift, Changes from Baseline and CTCAE grades

12.5.4.5 Vital Signs, Physical Findings and Other Observations Related to Safety

12.5.4.5.1 Prior and Concomitant Medication

Prior medication is defined as any medication that started and ended prior to Screening. Concomitant medication is defined as any medication starting on or after Screening. or medications that started prior to Screening and are ongoing at Screening.

All medications will be listed by product using PT and Anatomical Therapeutic and Chemical (ATC) codes (World Health Organization - Drug Dictionary Enhanced [WHO-DDE] March 2015 C format). A flag will be presented on the listing indicating whether the medication is prior or concomitant. Partial dates will not be imputed, but assumptions will be made as follows to assign to either prior or concomitant:

Date information	Assign as
Missing stop date	Concomitant
Partial date, e.g. --May2012, or -----2011. If month/year is the same as, or later than the month and/or year of Screening.	Concomitant
Partial date, e.g. --May2012, or -----2011. If month and/or year is earlier than the month and/or year of Screening.	Prior

Prior and concomitant medications will be listed by product. Concomitant medications will be summarized for the Safety Population showing the number (%) of subjects who used the medication at least once by product and by ATC 1st and 2nd levels and preferred drug name. Listings will display original dates (no imputation).

The data will be presented in the below outputs, the TFL number refers to the TFL number in the accompanying TFL shell document:

TFL number	Title
TABLES	
15.2.6.11.1	Summary of Prior Medication by Anatomical Therapeutic Classes (ATC) 1 and 2 – Safety Population
15.2.6.11.2	Summary of Prior Medication by Preferred Drug Name – Safety Population
15.2.6.12.1	Summary of Concomitant Medication by Anatomical Therapeutic Classes (ATC) 1 and 2 – Safety Population
15.2.6.12.2	Summary of Concomitant Medication by Preferred Drug Name – Safety Population
LISTINGS	
15.3.6.3	Listing of Prior and Concomitant Medication

12.5.4.5.2 Physical Examination

Physical examination data recorded at the Screening visit, Admission (Day -3) and at the day of Discharge (Day 6 or at the day of withdrawal for withdrawn subjects) will be listed by product. Subject's data with abnormal and abnormal clinically significant physical examination findings will be flagged. The number of subjects (%) with normal, abnormal and abnormal clinically significant results will be tabulated by body systems at Screening, Admission and day of Discharge.

Body weight recorded at Admission and day of Discharge; and body height recorded at the Screening visit will also be listed together with BMI. Descriptive statistics of body weight, body height and BMI (BMI will also be categorized as shown in Section 7.4 “**Categorical Variables**”), at Admission and Day of Discharge will be presented.

The data will be presented in the below outputs, the TFL number refers to the TFL number in the accompanying TFL shell document:

TFL number	Title
TABLES	
15.2.6.20	Summary of Physical Examination of Body Systems – Safety Population
LISTINGS	
15.3.6.10	Listing of Physical Examination Findings, Shift and Changes from Baseline

12.5.4.5.3 Vital Signs

Systolic and diastolic blood pressure, pulse rate and respiratory rate measured during the study will be listed by study visit, including low/normal/high results. Assessment after baseline will include change from baseline.

Descriptive statistics will be presented for systolic and diastolic blood pressure, pulse rate and respiratory rate at baseline, and on every subsequent day of the confinement period by product for each study day. Vital signs data will be summarized together with changes from baseline.

The data will be presented in the below outputs, the TFL number refers to the TFL number in the accompanying TFL shell document:

TFL number	Title
TABLES	
15.2.6.16	Summary of Supine Vital Signs – Safety Population
15.2.6.19	Summary of Weight and BMI Measurements – Safety Population
LISTINGS	
15.3.6.7	Listing of Vital Signs Data and Changes from Baseline

12.5.4.5.4 Spirometry

Spirometry parameters assessed during the study include:

- Measured forced expiratory volume in 1 second (FEV₁)
- Measured forced vital capacity (FVC)
- FEV₁/FVC

- Predicted FEV1
- Percent of predicted FEV1 (% pred)
- Predicted FVC
- Percent of predicted FVC (% pred)
- Measurement interpretation (categories: normal, abnormal, abnormal clinically significant)

The above data are collected at Screening, Day -1, and Day of Discharge (Day 6 or day of withdrawal). At Screening, data are collected one hour after having stopped smoking. On day -1 and Day 6, spirometry has to be done prior to smoking.

Spirometry predicted values will be standardized to the National Health and Nutrition Examination Survey III predicted set (**Hu and Cassano, 2000**).

Spirometry data values and normality evaluation will be listed by product and study day. Assessments performed after baseline will be listed together with change from baseline and shift in normality. Spirometry data from subjects who had significant clinical findings will be highlighted in listings.

Descriptive statistics will be presented for FEV₁(L), FEV₁ (% pred), FVC(L), FVC(% pred), and FEV₁/FVC at baseline, and Discharge by product, and overall. Spirometry data will be summarized together with changes from baseline (pre-bronchodilator), and the number and percentage of subjects with normal/abnormal/abnormal clinically significant results.

The data will be presented in the below outputs, the TFL number refers to the TFL number in the accompanying TFL shell document:

TFL number	Title
TABLES	
15.2.6.18	Summary of Spirometry Results – Safety Population
LISTINGS	
15.3.6.8	Listing of Spirometry Data and Changes from Baseline

12.5.4.5.5 Electrocardiogram

The ECG data will be obtained directly from the 12-lead ECG traces, i.e. not centrally read. These data include the PR, QT, and QT interval corrected using Bazett's formula (QTcB) and using Fridericia's formula (QTcF) intervals; QRS duration; and heart rate; and normality evaluation (normal, abnormal, clinically relevant, together with any PMI comments to the abnormality).

The baseline for the ECG data will be the Screening value.

ECG data values and normality evaluations will be listed by product and study day (Screening and Day 6) together with changes from baseline and shift in normality. ECG data from subjects which had significant clinical findings will be flagged in listings.

Descriptive statistics will be presented for ECG data at baseline, and Day 6 by product. ECG data will be summarized together with changes from baseline, and the number and percentage of subjects with normal/abnormal/abnormal clinically significant results.

The data will be presented in the below outputs, the TFL number refers to the TFL number in the accompanying TFL shell document:

TFL number	Title
TABLES	
15.2.6.17	Summary of ECG Measurements – Safety Population
LISTINGS	
15.3.6.9	Listing of ECG Data and Changes from Baseline

12.5.4.5.6 Assessment of Cough

Cough questionnaire is assessed on a daily basis from Day -1 to Day 6. Questionnaire details are reported in Section 7.2.6 “Cough Assessment”.

The number and % of subjects reporting cough will be summarized by product. The responses to the individual items, including the VAS evaluating the level of cough bother and 3 Likert scales measuring the intensity, the frequency of cough and the amount of sputum production will be listed and summarized on each day by study arm, for all subjects who filled in the questionnaire. The answers to the open question(s) related to any other important observation will be listed.

The data will be presented in the below outputs, the TFL number refers to the TFL number in the accompanying TFL shell document:

TFL number	Title
TABLES	
15.2.6.21	Summary of Cough Assessments Over Study – Safety Population
15.2.6.21.1	Summary of Cough Assessments by Study Day – Safety Population
LISTINGS	
15.3.6.14	Listing of Cough Assessment Results

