7.8.2 Assessment of Cough-VAS

Subjects will be asked to self-report and to assess the respiratory symptom ‘cough’ on a VAS, on three Likert scales, and with an open question. Assessment of cough will be conducted irrespective of the time.

Subjects will be asked if they have experienced a regular need to cough, e.g., whether they have coughed several times in the previous 24 hours prior to assessment. If the answer is ‘yes’, subjects will be asked to complete a VAS, 3 Likert scales and to answer the open question.

On the VAS, subjects will assess how bothersome their cough was during the previous 24 hours. The VAS ranges from ‘not bothering me at all’ to ‘extremely bothersome.’

Furthermore, subjects will assess the intensity and frequency of cough and the amount of sputum production during the previous 24 hours on Likert scales.

The intensity of cough will be assessed on a 5-point Likert scale ranging from 1 to 5, with 1 = very mild – 2 = mild – 3 = moderate – 4 = severe – 5 = very severe.

The frequency of cough will be assessed on a 5-point Likert scale ranging from 1 to 5, with 1 = rarely – 2 = sometimes – 3 = fairly often – 4 = often – 5 = almost always.

The amount of sputum production will be assessed on a 4-point Likert scale ranging from 0 to 3, with 0 = no sputum – 1 = a moderate amount of sputum – 2 = a larger amount of sputum – 3 = a very large amount of sputum.

Confidentiality Statement

Data and information contained in this document are considered to constitute trade secrets and confidential commercial information, and the legal protections provided to such trade secrets and confidential information are hereby claimed under the provisions of applicable law. No part of this document may be publicly disclosed without the written consent of Philip Morris Products S.A.

Finally, subjects will be asked to share any other important observations with the site collaborators about their coughing.

See [Appendix A](#) for the timepoints of assessment.

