12.5.4 Safety Analysis

In general, all safety data will be listed and tabulated on the safety population by product arm, using the approach described in section [12.1.3](#). Safety variables collected during Exposure Period will also be reported by product exposure.

Adverse event data will serve as the primary assessment of safety. Other safety variables monitored in this study include: respiratory symptoms (cough assessment VAS and Likert scales); vital signs (systolic and diastolic blood pressure, pulse rate, respiratory rate); spirometry; ECG data; clinical chemistry, hematology, concomitant medications, and urine analysis safety panel; physical examination.

The number and percentage of subjects with AEs and SAEs will be tabulated by system organ class and preferred term. Summaries will also be presented for AEs leading to withdrawal, AEs leading to death, AEs by relatedness to product exposure, AEs by severity, and laboratory AEs. Tabulations will be performed for both the number of subjects experiencing an event and the number of events.

The number and percentage of subjects with clinical findings will be tabulated by sequence for laboratory parameters. Shift tables showing change from baseline of clinical findings will be provided for: ECGs, physical examinations, and laboratory parameters (both shifts in normal ranges and toxicity grades). Descriptive statistics will be summarized by visit and change from Baseline for laboratory parameters, ECG, respiratory symptoms, and vital signs.

Confidentiality Statement

Data and information contained in this document are considered to constitute trade secrets and confidential commercial information, and the legal protections provided to such trade secrets and confidential information are hereby claimed under the provisions of applicable law. No part of this document may be publicly disclosed without the written consent of Philip Morris Products S.A.

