7.2.6 Cough Assessment

Subjects will be asked to assess the respiratory symptom ‘cough’ using a VAS, three Likert scale questions, and one open ended question on a daily basis during the confinement period (on Day -1 to Day 6) prior to 11:30 AM or at 06:29 AM \pm 1 hour on Day 6.

Subjects will be asked if they have experienced a regular need to cough, e.g., whether they have coughed several times in the previous 24 hours prior to assessment. If the answer is ‘yes’, subjects will be asked to complete questionnaire.

The VAS will assess how bothersome cough is to the subject ranging from ‘not bothering me at all’ to ‘extremely bothersome’, and this will be given a numeric value between 0 and 100, measured on a 100 mm scale.

Subjects will also be asked to assess the intensity and frequency of cough and the amount of sputum production on Likert scales as presented in **Table 7**.

Table 7 Cough Assessment Likert Scales

Question	Likert Scale
1 The intensity of cough	1 = very mild 2 = mild 3 = moderate 4 = severe 5 = very severe
2 The frequency of cough	1 = rarely 2 = sometimes 3 = fairly often 4 = often 5 = almost always
3 The amount of sputum production	0 = no sputum

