12.1.3 Descriptive Statistics

For continuous data, summary statistics will include the number of subjects (n), the number and percent of subjects with missing data, the arithmetic mean, arithmetic SD, median, first and third quartiles, minimum, maximum, and number; for log-normal data the geometric mean and geometric CV will also be presented. For categorical data, frequency counts and percentages will be presented. Data listings will include all subject level data collected unless otherwise specified. Summary statistics and statistical analyses will generally only be performed for subjects included in the relevant analysis population. For the calculation of summary statistics and statistical analysis, unrounded data will be used.

Summaries on the Safety Population will be produced by actual exposure. Subjects who tested the product but were discontinued before randomization will be shown in a separate column /table.

The following product labels will be used throughout the TFLs (**Table 17**):

Table 17: Product Labels		
Product	Format used in TFLs	Order in TFLs
Carbon Heated Tobacco Product	CHTP	1
Conventional cigarettes	CC	2

The following stratification labels (**Table 18**) for the TFLs will be used:

Table 18: Stratification Labels	
Stratification Factor	Definition
Sex	male
	female
Daily CC consumption (per day)	<10 ¹
	10-19
	>19

¹ Note that due to inclusion criteria for the study there should not be any subjects with daily CC consumption < 10, therefore this category will not be presented unless there is sufficient data for analysis/presentation (see Section 12.1.5.1 "Insufficient Data for Analysis/Presentation").

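### The daily cough VAS and Likert summaries cover only subjects reporting regular cough that day, so they can understate or reverse a real change unless shown over everyone asked

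*SAP*

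**What the plan says.** Protocol 7.8.2 first asks whether the subject had a regular need to cough in the previous 24 hours, giving coughing several times as its example. Only after a 'yes' does it say that "subjects will be asked to complete a VAS, 3 Likert scales and to answer the open question". SAP 7.2.6 repeats the condition: after a 'yes', "subjects will be asked to complete questionnaire". The VAS is numeric: "this will be given a numeric value between 0 and 100, measured on a 100 mm scale".

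SAP 12.5.4.5.6 sets the analysis:

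- Timing: "Cough questionnaire is assessed on a daily basis from Day -1 to Day 6".
- Incidence: "The number and % of subjects reporting cough will be summarized by product".
- VAS and Likert items: "listed and summarized on each day by study arm, for all subjects who filled in the questionnaire".

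The outputs are one table over the study and one by study day, both on the Safety Population. SAP 12.1.3 gives the statistics for continuous data, including "the number and percent of subjects with missing data, the arithmetic mean, arithmetic SD, median"; categorical data get counts and percentages. SAP 12.1.5 refers questionnaire imputation to Section 7.2, and 7.2.6 has no rule for a 'no'. Protocol 12.1.4 summarises evaluable data without imputation.

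Protocol 12.5.4 also promises that "Descriptive statistics will be summarized by visit and change from Baseline for laboratory parameters, ECG, respiratory symptoms, and vital signs". SAP 12.5.4.5.6 mentions no change from baseline for cough, and SAP Section 9 does not list its removal.

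**The concern.** A 'no' to the filter question is an answer, not a missing value, yet it drops the subject from that day's severity summary. The subset is formed afresh at each of seven assessments (Day -1, then Days 1 to 6). The Day -1 and Day 1 reports are made before assigned product is used. Those of Days 2 to 6 follow its use, so from then on membership of the subset is itself a post-randomisation outcome.

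If mild cough clears after switching, the remaining responders are the worse coughers and the mean VAS is pushed up. If switching provokes new mild cough, the mean is pulled down. Either way the daily course of the mean, and the two columns read side by side, may not reflect what happened in the randomised groups.

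Cough by VAS and Likert scales is a named secondary safety endpoint. Protocol 7.8 also says that symptoms on the questionnaires and the cough VAS need not be recorded as adverse events, because these instruments will be analysed in the final report. The investigator may still record them, but the cough table is the stated reason for not requiring it, so that table should be readable.

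**Working it through.** The plan states no cough rate, VAS level, power or sample size for this endpoint, so there is no figure of its own to reproduce. The check is whether the mean among responders can mislead, and by how much, under assumed values. From the documents come the arm size (about 40), the VAS range (0 to 100) and the denominator (subjects who filled in the questionnaire). Everything else is assumed. The all-subject mean scores a 'no' as 0, which is also an assumption.

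**Example 1: two groups of coughers.** At baseline 20 of 40 subjects cough, 10 at VAS 15 and 10 at VAS 50.

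- Responder mean: (10×15 + 10×50)/20 = 650/20 = 32.5.
- All-subject mean: 650/40 = 16.25.

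Later every cougher improves by 5 points and k of the 10 mild coughers stop.

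- Responder mean: [10×(10−k) + 10×45]/(20−k) = (550 − 10k)/(20 − k).
- All-subject mean: (550 − 10k)/40.

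| k | Responder mean | All-subject mean |
|---|---|---|
| 0 | 27.5 | 13.75 |
| 4 | 31.9 | 12.75 |
| 5 | 33.3 | 12.50 |
| 10 | 45.0 | 11.25 |

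The responder mean exceeds its baseline when 550 − 10k > 32.5×(20 − k), that is k > 100/22.5 = 4.4, so from k = 5. At k = 10 nobody is worse and the share coughing has halved from 50% to 25%, yet the responder mean rises from 32.5 to 45.0. Read backwards, the same figures show the safety risk: ten subjects worsen by 5 points and ten new mild coughers appear, and the responder mean falls from 45.0 to 32.5.

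Tabulation does not avoid the problem. At k = 10, if the worse group keeps the same Likert category, it goes from 10/20 (50%) to 10/10 (100%) of responders while remaining 10/40 (25%) of the arm.

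**Example 2: uniform improvement.** Let a latent score be Normal with mean μ = 15 and SD σ = 20, with cough reported only above a threshold t. Every score then falls by 15 points, so μ = 0. The responder mean is μ + σφ(a)/[1 − Φ(a)], with a = (t − μ)/σ.

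For t = 10:

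- Before: a = −0.25, giving 15 + 20×0.387/0.599 = 27.9.
- After: a = 0.5, giving 20×0.352/0.309 = 22.8.

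Multiplying by the share coughing gives the all-subject means, 16.7 and 7.0. A simulation of 2,000,000 draws per setting gave these results:

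| t | Share coughing | Responder mean | All-subject mean |
|---|---|---|---|
| 0 | 77% to 50% | 22.8 to 15.9 (−30%) | 17.6 to 8.0 (−55%) |
| 10 | 60% to 31% | 27.9 to 22.8 (−18%) | 16.7 to 7.0 (−58%) |
| 20 | 40% to 16% | 34.3 to 30.5 (−11%) | 13.8 to 4.8 (−65%) |

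Here the direction is right but the improvement is understated.

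**The case against.** The strongest reply is that the SAP already gives a two-part description: how many cough, and how badly among those who do. The same paragraph plans the number and percentage reporting cough, and the continuous tables carry n. In Example 1 a reader would see n fall from 20 to 10 as the mean rose. That stands, and it limits the harm. It does not put the scores on a stable denominator.

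Several stronger readings are tempting, and the documents do not support them:

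- *The arms are formally compared on different subjects.* SAP 12.5.4.5.6 has no test, model, difference or confidence interval, only side-by-side description. Adverse events are the primary safety assessment (Protocol 12.5.4), and the cough tables are in neither the safety-reporting list nor the topline list (SAP 13.2, 13.3).
- *The Likert items are averaged.* The SAP says only that they are summarised. A mean follows from SAP 12.1.3 for the VAS alone, and the separate shell document may settle the rest.
- *A 'no' means VAS 0.* The question is about regular cough. A subject with occasional cough may properly answer 'no', and sputum is not asked about at that step. Scoring 0 is an imputation, and it sits awkwardly with the protocol's no-imputation rule.
- *The SAP plans a change from baseline restricted to subjects coughing on both days.* It plans none; only the protocol mentions one.

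**Conclusion.** The point holds as a weakness in a descriptive safety table. The severity items are summarised over a subset that is re-formed daily and, once product use starts, depends on a post-randomisation outcome. The incidence count and n make this visible but do not remove it.

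The size cannot be known from the documents. Under the assumed values the responder mean ranges from understating a real improvement to reversing it. A reader might infer that reversal is the expected result. It is not: in Example 1 it needs at least 5 of 10 mild coughers to stop, and in Example 2 it does not occur. The all-subject comparison figures rest on scoring a 'no' as 0.

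The primary analysis is unaffected, and nothing in the documents makes a decision depend on this table. The change is still worth making, because the endpoint is named, its analysis is the stated reason for not requiring adverse event recording, and the data needed are already collected.

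**What to change.** Amend SAP 12.5.4.5.6 as follows:

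1. Tabulate each item by day and arm over all subjects who answered the filter question, with an explicit 'no regular cough' level. Banded VAS and Likert categories with n/N would serve. Keep that level separate from the sputum scale's own zero, and add it below the intensity and frequency scales, which start at 1.
2. Show the daily percentage reporting cough beside these tables.
3. Keep the responders-only VAS and Likert summaries, labelled as conditional on reporting cough.
4. If an all-subject VAS mean with 'no' scored as 0 is added, make it supplementary and state the assumption.
5. State whether the Likert items are tabulated or averaged.
6. Either restore the change from baseline promised in Protocol 12.5.4, on the all-subject basis so that subjects moving into or out of cough are counted, or list its removal in SAP Section 9.

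The cost is SAP wording, one derivation rule and slightly larger tables; no new data are needed. The drawback is a large 'no regular cough' category, or a spike at zero in any all-subject VAS summary, so the median and quartiles should be read with the mean.
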